4.6 Recruitment

All recruitment will be completed online: this protocol does not involve SRV engagement in recruitment or intervention delivery. Participants will be recruited via online ads placed on key social media websites (e.g., Facebook, Instagram, Snapchat, Grindr, etc.). The online ads will show visual representations of young male couples, in a range of race/ethnicities and will be titled: “*We Prevent.*” People who click on the advertisement will be taken to the Survey Gizmo screener webpage that provides basic information on the study: this will be referred to throughout the protocol as the ‘landing page’. On the landing page will be basic information on the study processes and a “do you consent to be screened?” question; if participants click “yes” they will be screened for eligibility.. All recruitment will be tracked in the screener with the question “How were you directed to the study website?”

This study will also use Cameo as part of its online recruitment strategy. Cameo is a website that allows users to pay celebrities to create short 20-second videos and deliver a particular message of the user’s choice. Once the video is created and paid for, Cameo delivers the video file to the user. Study staff will upload the video to the social media sites already being used for recruitment. The script will only contain information about the study: “Hi, this is (insert celebrity name) and I want to tell you about an HIV prevention study from the University of Michigan. This study is aimed at young gay and bisexual men who are in their first relationships. If you are eligible, you will take a few surveys and get mailed an at-home HIV testing kit. Click on the link to see if you’re eligible!”

4.7 Informed Consent

For all phases of the study, there are two points of consent: 1) consent for screening for eligibility, and 2) consent to participate in the study. When participants click on the “interested in participation?” button, they are taken to the next page of the website. This page contains the first informed assent/consent survey (for screening). After reading the consent script participants can click on “agree” or “disagree”. If they click agree they will be taken to the eligibility screener (a Alchemer survey) and if they disagree they will be taken to a page that thanks them for their interest and links them to the CDC HIV toolkit page. Those who are ineligible will be asked if they want to provide their contact information to be contacted about future research opportunities. The consent/ decline decision will be recorded in the data base linked to a participant unique ID, that can then be linked to their data to allow an electronic record of consent/ assent for all participants. For Phase I, after taking the eligibility screener (see below), those who are eligible will be taken to a page that shows the second consent/ assent form that explains the specific study activities for which they are being recruited. After reading the informed consent form the participant can consent/assent or decline in the same manner as the eligibility consent. For Phase III, participants will complete the eligibility screener in Alchemer, and if eligible and consent to participate in the study, will be automatically re-directed to a

SMART registration page where they will enter their contact information and be instructed to download the We Prevent-specific SMART app. For participants who are invited by the index partner and are eligible to participate, we will schedule an informed consent phone call immediately following their screening into the study. We will provide information about the study procedures to ensure they understand that they will be participating to a lesser extent than the index partner but still with their partner.

Assessing for decisional capacity. The study staff reviews the informed consent/assent to make a formal assessment of the youth's decisional capacity and ability to provide consent/assent prior to each video-conferencing session, using a 2-step process. First, the staff members determine if the person understands the study goals by asking "Can you tell me what this study is about?" In step 2, potential participants will be asked questions designed to assess their capacity to understand, appreciate, reason with, and express a choice about participation in our specific protocol. We will use a modified version of the widely used Evaluation to Sign Consent Form in which participants are asked to: **1)** name things they will be expected to do during the study; **2)** explain what they would do if they no longer wished to participate in the study; **3)** explain what they would do if they experienced distress during the study; and **4)** identify potential risks for participating in the study. Potential participants will be enrolled only if they are able to provide clear and correct answers to each of these items, without prompting or correction.

Waiver of parental consent. We will request that the UNC-CH IRB as the central IRB (IRB of Record) grant a waiver of parental consent to participate in this research study for youth participants who are 15 to 17 years of age. The research team has been granted waivers of parental permission for all prior studies with sexual minority youth. Under 45 CFR 46.408 (c), an IRB has the authority to waive parental permission if it determines that "a research protocol is designed for conditions or a subject population for which parental or guardian permission is not a reasonable requirement to protect the subjects" and "an appropriate mechanism for protecting the children who will participate as research subjects is substituted" and "that the waiver is not inconsistent with Federal, State, or local law." A waiver of parental permission for studies with lesbian, gay, bisexual, transgender, and questioning (LGBTQ) youth that do not involve greater than minimal risk is a common practice among researchers working in the area of gay and lesbian health/mental health. This is done to avoid the selection biases operating in only recruiting youth whose parents are both aware of and comfortable with their sexual orientation. Commonly youth have explored their sexual orientation without their parents' knowledge as the youth struggle with issues of disclosure and its consequences within the social, religious, and economic context of their families. A requirement for parental permission in this type of study could not only affect a person's willingness to participate but could also potentially impact the ability of researchers to engage in this type of research with sexual minority youth.

If the purpose of requiring parental permission as stated in CFR is to protect the minor subject, then requiring parental permission for youth in these circumstances is not a reasonable requirement. Additional privacy protections are provided in that all assessments, notes, reports, and other records will be identified by only a coded number to maintain participant confidentiality. These records and any forms that do contain identifying information (e.g., consent/assent forms, contact information) will be kept in a locked, limited access area (such as a locked file cabinet) at the participating site.

The study is requesting waiver of written informed consent from adult participants (18 years old and above) See sections 12.5 through 12.6 for additional information regarding waivers of written informed consent.

4.8 Screening and Registration

Participants will have completed the following process: clicking on a banner advertisement, learning about the study via the study landing page, consenting to be screened for eligibility, answering eligibility questions on a Alchemer survey, reading the informed consent/assent form and consenting/ assenting to participate. For participants in Phase III, after screening eligible, participants will be redirected to a SMART linked web page where they will enter their contact information, which will then be automatically populated into SMART and verified. Study staff members will verify eligibility for all participants who screen eligible and provide consent. Once their eligibility is confirmed, participants will be sent instructions to download the SMART study application and all follow-up activities will be conducted through SMART. If the participant is randomized into the intervention arm and chooses to participate with their partner, the invited partner will be emailed a link to the eligibility screener. If they screen eligible, study staff will schedule an informed consent phone call with the invited partner (described above in the informed consent section). Contact information for the invited partner will be requested in the brief baseline survey and will be stored in a password-protected file within Box or Microsoft OneDrive.

5.0 STUDY PROCEDURES

5.1 Enrollment Procedures

Phase I: The same processes will be used for Task 1 and Task 3. They will not operate in parallel. Task 1 will be completed first, with the data from the in-depth interviews being used to develop the intervention manual. After development of the manual, we will engage in Task 2. Feedback from Task 2 will then be incorporated into the manual. Once both Task 1 and 2 are complete, then we will begin Task 3, which involves cognitive interviews with an additional 10 participants. Once the eligible participant has completed the screener and provided their contact information, a study staff member will email them with a link to the brief online survey in Alchemer. Once they have completed the brief survey, we will contact them to schedule the interview for Task 1 or Task 3 (dependent on what they are recruited for). Before the interview, the study staff member will review the consent process to ensure they understood their rights and the details of their participation. Alchemer has a business partner HIPAA agreement with Emory. Alchemer servers are HIPAA-compliant. The time between eligibility screening and completing the survey and interview will be tracked through SMART, and weekly reminders will be sent out (via the participant's choice of SMS or email) to remind them to complete the survey and/or the in-depth interview.

Phase II: If the prospective participant screens eligible, they will enter their and their partner's contact information directly into the Alchemer screener. After email and phone validation, the invited partner will receive an emailed link to the screener. If eligible, the invited partner will also provide and verify their contact information. After both partners have screened eligible, verified their data and their contact information, both participants will be emailed a link to complete the baseline survey and all subsequent study activities. Once they have both completed the baseline survey, they can opt-in to the at-home STI testing process and schedule the relationship skills session that will be conducted via Zoom or VSee video-chat software.

Participants will then be mailed STI testing kits. Once they have completed the relationship skills session, they will be mailed HIV testing kits and scheduled for their CHTC session. Surveys will be completed at Baseline and 1-month follow-up. At-home STI testing will be offered at Baseline. With regard to the baseline survey, participants have four weeks to complete the survey from the time the screen eligible. Reminders will be sent to ensure that participants are aware of this study activity. If the baseline is not complete by either of the partners within the four weeks, the couple will be study-stopped. If only one of the participants completes the baseline survey, study staff will continue to follow that participant with the 1-month follow-up survey.

Phase III: If the prospective participant screens eligible, they will enter their contact information into a registration page connected to SMART. After completing the registration page, participants will be instructed to download the SMART app where all subsequent study activities will take place. Participants will be randomized in DFExplore after completing the Baseline survey. Participants randomized to the control arm will complete the study entirely on their own. Those randomized into the intervention arm will have the option to participate alone or with their partner. If they choose to participate with their partner, their partner will be screened for eligibility, consented, and complete a brief survey (not the full baseline survey). The invited partner will not be put into SMART and the only information we will collect is the screener, consent and brief survey data, along with a satisfaction survey after the CHTC session. For invited partners who screen eligible and complete the brief survey, study staff will consent them over the phone prior to the CHTC session. Index participants will complete surveys at Baseline, 3-month, 6-month, and 9-month follow-up. They will be mailed STI kits at Baseline and the 6-month follow-up.

To ensure representation of racial/ethnic minorities, we have a target of 50% in all phases of the study be racial/ethnic minority participants. If enrollment of racial/ethnic minority participants drops below 50%, we will explore additional recruitment strategies

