In Phase III, the intervention-arm index partner will schedule their CHTC + Relationship Skills session (with their partner) or their CTR + Relationship Skills session (on their own). The session will be conducted via the HIPAA-compliant Zoom video-chat software. The test kit package containing oral fluid tests (OraQuick) will be mailed to the participant's residence of choice. Participants who chose to do CHTC + Relationship Skills and are in long distance relationships or have separate living arrangements from their partner will be sent their test kits separately. All participants will be informed to have their HIV testing kits present. The session will be conducted by a counselor who is trained in CHTC and CTR. Sessions will last approximately 45 minutes. In the CHTC + Relationship Skills session, both members of the couple will conduct their own test and read their own results – together – as directed by the counselor. In the CTR + Relationship Skills session, the participant will conduct their own test and read their results as directed by the counselor. Participants will be asked to show the counselor their test result for confirmation of reading accuracy. Post-test counseling will focus on dyadic prevention messages and will revisit the couple HIV risk concerns and sexual agreements in light of their test results. The counselor will record each participant's HIV test results in the SMART admin portal. The goal of both CHTC + Relationship Skills session and CTR + Relationship Skills session is to facilitate the participant in thinking critically about the management of HIV in their relationship and to guide them in making a prevention plan that best suits their relationship needs, context, and risks. It is easy to imagine that when a positive result is given that the CHTC + Relationship Skills session may devolve into a support session for the new positive. We have trained our counselors to keep focusing on the dyad in this situation, and while a focus on the immediate needs of the positive is required, the discussion remains focused on how the couple can work together to keep the positive partner healthy and to reduce transmission risks within the relationship while also meeting both partner of the couples' needs.

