For preliminary positive results for any participant, at the end of the video CHTC + Relationship Skills or CTR + Relationship Skills session, the participant will be counseled on the need for timely linkage to care. Within 48 hours, the counselor will then send a confidential email to the participant(s) individually providing the contact information for providers in their area who can provide confirmatory testing and linkage to care. Then within 1 week of the session, study staff will follow up with the participant(s) over the phone or Zoom to see if an appointment was made. If not, staff will urge participants to make an appointment as soon as they can and will emphasize the importance of confirmatory testing and linkage to care. Study staff will then follow up within 1 month of the session and 3 months to (1) confirm an appointment was scheduled, 2) to confirm the appointment was attended, 3) to report confirmatory results, and 4) assess linkage to care.

Satisfaction survey: Within one week of the CHTC + Relationship Skills or CTR + Relationship Skills session, each participant will receive an email asking them to complete a short satisfaction survey: the survey will include questions regarding satisfaction with the home testing process, logistics (i.e., length of session), content of session, and reactions to testing process (i.e. ease, comfort), in addition to willingness to utilize the intervention in the future. If the participant's partner also took part in the session, they are also sent a satisfaction survey.

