Participants who learn that they are HIV-positive may be distressed to learn of their health condition. This poses the greatest emotional and physical risk to participants in the research study. The informed consent documents will outline the HIV testing process, stating that results will be delivered the same day, and study staff will explain in full what a positive, negative or indeterminate HIV test result mean before conducting the HIV tests. The counselor will assess the individual's readiness to receive both the HIV test and the result, following standard HIV testing guidelines. All study counselors are experienced in the delivery of HIV test results, and will follow standard clinic guidelines for results delivery. Individuals (or couples) receiving positive HIV test results will be provided with counseling and referrals to care that are appropriate to their economic situation (e.g. those eligible for Ryan White Care will be linked to the appropriate services). All those receiving a positive result will be given a full list of local service providers.

It is also possible that having a discussion about past sexual behaviors with a participant's partner might lead to subsequent conflict, or even violence, within their relationship. To ameliorate this risk, we propose to screen out those with a history of intimate partner violence (IPV) in the relationship. It is possible that new, incident, IPV may occur. This will be recorded through questionnaires on the surveys at each study visit. Individuals reporting IPV will be offered the opportunity to also meet individually with the study counselor, and will be provided with referrals to local services. All study participants, regardless of whether or not they report IPV, will be given a local resource guide that outlines programs and sources of support for people dealing with a wide range of circumstances (e.g., mental health, suicide), such that no partner will be able to identify that the other has reported IPV to study staff.

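### Invited partners in the Phase III joint session have no scheduled question about partner violence afterwards, and the protocol contradicts itself on what is recorded about them

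*Protocol*

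**What the plan says.** Protocol Section 5.4 lets intervention-arm participants attend alone, with their partner, or both in turn. A partner who joins is mailed an HIV self-test kit and, under Section 6.6, tests himself in the joint session under the counselor's direction.

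On data collection, Section 5.1 keeps the invited partner out of SMART and states that "the only information we will collect is the screener, consent and brief survey data, along with a satisfaction survey after the CHTC session". Follow-up is described for one member of the couple only: "Index participants will complete surveys at Baseline, 3-month, 6-month, and 9-month follow-up".

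On harm, Section 12.3 says that discussing past sexual behavior with a partner "might lead to subsequent conflict, or even violence, within their relationship". It continues: "It is possible that new, incident, IPV may occur. This will be recorded through questionnaires on the surveys at each study visit".

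On HIV results, Section 6.6 has the counselor enter each participant's "HIV test results in the SMART admin portal". After a preliminary positive in any participant there is an individual email within 48 hours and a staff contact within 1 week. Then: "Study staff will then follow up within 1 month of the session and 3 months", to establish whether an appointment was made and kept, the confirmatory result, and linkage to care.

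**The concern.** Two people are exposed to the joint session, but the one active method named for finding new violence reaches only one of them. Section 6.4 describes the violence items as covering the respondent's experiences. If the index participant is the source of the harm, the person harmed is the one who is not asked. The individual counselor meeting in Section 12.3 is offered to those who report violence, so a partner who is never asked has less chance of being offered it.

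Phase II does not fill the gap. It planned surveys of both partners at baseline and 1 month, but Section 3.2 reports that nobody completed a session. Phase III would thus be this project's first delivery of the joint session, with follow-up of the partner removed.

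The second issue is one of records. Staff who follow Section 5.1 to the letter would have nowhere to enter a partner's HIV result or the follow-up that Section 6.6 requires.

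**Working it through.** The plan states no figure to reproduce. The check sets the sections side by side and counts scheduled contacts.

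**Step 1. Violence assessments scheduled after the joint session**

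| Instrument | Index participant | Invited partner |
|---|---|---|
| Screener and baseline or brief survey (5.1) | Before the session | Before the session |
| Satisfaction survey, within one week (6.6) | Yes; no violence item listed | Yes; no violence item listed |
| 3-, 6- and 9-month surveys (5.1), with violence items (6.1, 6.4, 12.3) | 3 | 0 |

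The satisfaction survey content in Section 6.6 is the home testing process, logistics, session content, reactions to testing, and willingness to use the intervention again. Section 6.1 adds a chance to give feedback on the sessions, which is not a question about violence. The index count of 3 is a maximum. Section 5.4 asks for the initial session within four weeks of enrollment but sets no limit for a joint session held second.

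**Step 2. Other routes by which harm to a partner could surface**

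- Section 4.5 excludes couples in which either member reports violence in the past 6 months. This screens history, and Section 12.3 accepts that new violence may still occur.
- Section 5.3 covers conflict or threat that the counselor sees in the session. The risk in Section 12.3 is of later conflict.
- Sections 9.3 and 10 require action and reporting, including for delayed physical harm, once it comes to staff attention. Neither schedules a question to the partner.

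So routes exist, but after the session all of them depend on someone volunteering the information.

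**Step 3. HIV result and follow-up**

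- Section 6.6 applies to any participant and names the joint session, so its natural reading includes the invited partner. The result is seen in session and followed to 3 months.
- Section 6.6 places the result in the SMART portal and gathers further information at 1 week, 1 month and 3 months.
- Section 5.1 says the partner is not in SMART and lists only screener, consent, brief survey and satisfaction data.

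Read literally, these statements cannot all hold.

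**Step 4. Kits sent but not used in a session**

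Section 5.4 mails a kit to the partner before the session. Section 6.1 sends an at-home testing survey through SMART when a kit has been sent and no session follows within 45 days of enrollment. A partner outside SMART does not receive it.

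**Step 5. Scale**

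The sample is 320 index participants (Section 3.2), allocated 1:1 (Section 5.5): 320 × 1/2 = 160 in the intervention arm. If a proportion u bring a partner to a joint session, the number of partners is 160 × u. The documents do not give u. As assumed values, 25% gives 40, 50% gives 80 and 100% gives 160. The Phase II experience means that values near 0 cannot be excluded.

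**The case against.** The strongest reply is that the partner's limited role is deliberate and disclosed. Section 4.7 tells him that he takes part to a lesser extent than the index participant. On this view, further follow-up is a design preference. That answers a demand for full follow-up surveys. It does not answer the mismatch between a risk that Section 12.3 attaches to the couple and a detection method that covers one member.

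A second reply is that Section 5.1 is being read too literally. Taken at its word, it would also rule out the audio recording of sessions (Section 8.8.2), which is plainly planned. Partner contact details sit in a protected file outside SMART (Section 4.8), case report forms hold laboratory results and adverse events (Section 8.8.1), and the SMART portal works without the mobile app (Section 9.1). This stands in part: the SMART issue is a conflict of wording to be resolved, and does not prove that no record can exist. The violence gap does not rest on that sentence alone, because it follows from who receives the follow-up surveys.

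A reader might go further and infer that harm to partners goes undetected altogether. The documents do not support that: a positive result is seen by the counselor and followed under Section 6.6, and Sections 5.3, 9.3 and 10 provide in-session and spontaneous-report routes. A reader might also try to estimate how many violent events would be missed. That needs an uptake and a violence rate that the documents do not contain, and it would assume that spontaneous reporting yields nothing. Nor do the documents show that an unsupported safety claim is planned: neither Protocol Section 11.2 nor the SAP includes a Phase III safety analysis.

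**Conclusion.** The point holds in limited form. Invited partners have no scheduled assessment for partner violence after the joint session, against up to three for each index participant. Detection in partners rests on in-session observation or on harm coming to staff attention. Separately, Section 5.1 conflicts with Section 6.6 on whether the partner's HIV result and follow-up information are recorded, and the SMART-delivered testing survey in Section 6.1 does not reach partners who are mailed a kit.

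Between 0 and 160 partners are affected, depending on an uptake that is not stated. The conclusion assumes that the satisfaction survey contains only what Sections 6.1 and 6.6 list, and that the follow-up procedure for any participant in Section 6.6 is meant to include invited partners.

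**What to change.** Add the violence items already used in the index surveys to the satisfaction survey that the partner already receives after the joint session.

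Reconcile Protocol Sections 5.1, 5.4, 6.1, 6.6, 10 and 12.3 so that they state:

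- where the invited partner's HIV result and the contacts after a preliminary positive are recorded, whether in SMART or on a case report form;
- whether the at-home testing survey applies to partners who are mailed a kit and, if so, how it reaches them outside SMART;
- that reporting of untoward effects under Section 10 covers invited partners.

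This proposes no new clinical rule. The responses to a report of violence stay as they are in Sections 9.3 and 12.3, and the resource guide in Section 12.3 already goes to all study participants.

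The cost is a few more items for the partner, revised consent and protocol wording, and staff time to handle any reports through those procedures. Some partners may be minors and the link is emailed, so the private-completion precautions in Section 12.3 should be stated to apply to this survey too.
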